9.2.2.2 Time Periods and Dates

The study period is determined by the launch date of linaclotide and subsequent uptake. The study period starts on the date of linaclotide commercialisation in each of the countries: in UK in May 2013, in Spain in September 2014, and in Sweden in February 2013.

The end of the study period is defined by the last day of patient records in the available data cut, currently planned for 31 December 2017, to allow for sufficient follow-up time (long-term use) to have

the opportunity to accrue a sizable number of subjects for descriptive purposes, and for subpopulations of interest (those with potential off-label use and potential for abuse/excessive use). Please refer to the Study Size and Data Analysis sections below.

[figure not shown]
Additionally, the database's lag time (for collected data to be available in each database, estimated as up to 8 months) needs to be factored in to determine when data will be available.

Index date (or cohort entry date) will be defined as date of the first prescription (UK) or dispensation of linaclotide (Spain and Sweden). Baseline period will be the ≥ 12 -month period before index date.

The follow-up period for each study subject will be the time from the index date to the earliest of the following dates (end of follow-up date; one day is the minimum follow-up; Figure 1):

- End of the study period for follow-up
- Disenrollment from the database (date of transfer out of the practice)
- Date of last data collection
- Death
- 1.5 times the number of days of linaclotide supply after the expiry of the last linaclotide prescription during the study period (for a total of 2.5 times the last prescription duration) plus one additional day when a potential discontinuation could be assessed (please refer to section 9.3.3 Linaclotide Treatment Outcomes below)

Figure 1. Study Periods Linaclotide DUS

9.3. Variables

9.3.1. Variables to Identify Subgroups of Interest

In order to identify the subgroups of patients of interest, the following variables will be used:

- Age
- Gender
- Pregnancy and breast-feeding (when available)
- Diagnosis of IBS and type
- Chronic constipation
- Mechanical gastrointestinal obstruction or IBD
- Hepatic impairment, chronic kidney disease or chronic renal failure
- Cardiovascular disorders or risk factors—i.e., cerebrovascular disease, coronary artery disease, angina, myocardial infarction, heart failure, arrhythmias, use of antiarrhythmic drugs, hyperlipidaemia, or use of lipid-lowering drugs
- Hypertension or use of antihypertensive drugs
- Diabetes
- Obesity and eating disorders (anorexia nervosa, bulimia) that are suspected conditions related to potential for abuse or excessive use—e.g., use for weight loss or as laxative

9.3.2. Variables at Baseline

Patients included in the DUS will be described according to their characteristics at index date, using data from the baseline period, from diagnoses, procedures and prescription information from each data source:

- Age (as continuous variable and categories <18, 18-65, ≥65 years)
- Gender
- Diagnosis of IBS and type ¹
- Comorbidities:
 - o Cardiovascular disorders or risk factors—i.e., cerebrovascular disease, coronary artery disease, angina, myocardial infarction, heart failure, arrhythmias, use of antiarrhythmic drugs, hyperlipidaemia, or use of lipid-lowering drugs
 - o Hypertension or use of antihypertensive drugs
 - o Diabetes
 - o Hepatic impairment
 - o Chronic kidney disease or chronic renal failure
 - o Inflammatory bowel conditions (i.e., Crohn's disease, ulcerative colitis, microscopic colitis)
 - o Mechanical gastrointestinal obstruction
 - o Any psychiatric disorder, as well as:
 - Depression diagnosis
 - Anxiety diagnosis
 - o Food intolerance (e.g., lactose)
 - o Celiac disease
 - o Cancer (e.g., colon)
 - o Bile salt malabsorption
 - o Immunodeficiency

¹ When possible, proportion of IBS-C.

- Obesity and eating disorders (anorexia nervosa, bulimia)
- Medications: the three most commonly prescribed medication groups in addition to the following, if not included (Only about half of IBS-C patients are expected to be on prescribed medication, but the majority of patients are expected to be self-treated [Wilson et al., 2004].):
 - Laxatives (i.e., bulk-forming laxatives, stimulant laxatives, faecal softeners, and osmotic laxatives) (Concomitant use of laxatives was described among one-third of the antispasmodic mebeverine users and it was associated with increased odds of hospitalisation [Goettsch WG, 2004].)
 - Antispasmodics (i.e., anti-muscarinic agents and direct-action smooth muscle relaxants)
 - Prokinetic drugs
 - Antidepressants (i.e., tricyclic antidepressants, selective serotonin reuptake inhibitors, serotonin-norepinephrine reuptake inhibitors, and monoamine oxidase inhibitors)
 - Antibiotics
 - Calcium and aluminium-containing antacids
 - Magnesium-containing antacids
 - H2 blockers
 - Proton pump inhibitors
 - Analgesic drug classes:
 - Non-steroidal anti-inflammatory drugs
 - Opioids
 - Other analgesics
- Other variables:
 - History of digestive surgery (especially history of cholecystectomy)
 - Gastroenterology clinic visit (Spain and Sweden) or referral (UK)
 - Bacterial/viral/parasite lab information, when available (positive versus negative or no information)

For prevalence of chronic comorbidities, prior diagnoses, or history of digestive surgery at index date, the patient's entire medical history will be explored.

9.3.3. *Linaclotide Treatment Outcomes*

Secondary outcomes of this study will be linaclotide treatment patterns. The linaclotide exposure information is characterised by the linaclotide days of supply. Days of supply will be ascertained from the prescription/dispensation information recorded in the databases and the recommended dose (one capsule of linaclotide 290 µg taken once per day) and calculated by dividing the quantity prescribed/dispensed by the daily dose. Days of supply of one prescription/dispensation are expected to be around 28 days since the 28-capsule pack will be the most widely used package size. If package size is unknown, then the median duration for patients with this information will be used (and if no median can be estimated then 28 days will be used).

Linaclotide prescription patterns of interest are:

- Discontinuation of linaclotide: defined as no prescription of linaclotide in the period of 1.5 times the number of days of supply of the last linaclotide prescription following its expiry date (Sikka et al., 2005; Peterson et al., 2007): for example, for a 28-day prescription, no new prescription in the 43 days after the expiry date of the prescription supply. The date of discontinuation is the day after the date of expiry of the last linaclotide prescription. Time to discontinuation (permanently during the study period or temporarily) is the interval between the date of the first linaclotide prescription and the date of discontinuation. Discontinuation

will be reported separately for those who permanently discontinue during the study period and for those who discontinue temporarily and subsequently restart on linaclotide (see below).

- Switching from linaclotide to laxatives, antispasmodics, prokinetics, or antidepressants without prescription of linaclotide: defined as a prescription of laxatives, antispasmodics, prokinetics, or antidepressants that starts while on treatment with linaclotide and continues after the date of the linaclotide discontinuation. The date of switching is the date when the new prescription of laxatives, antispasmodics, prokinetics, or antidepressants is issued followed by linaclotide discontinuation. Time to switching is the interval between the date of the first linaclotide prescription and the date of switching.

To be able to define linaclotide discontinuation and switching at the end of the study period, it is necessary to have enough study period for follow-up after the expiry of the last linaclotide prescription. This time at the end of the study corresponds to the gap tolerated between prescriptions that could occur if the patient is on treatment but also hospitalized or travelling. This grace period is defined as 2.5 times the number of days of supply of the last linaclotide prescription (the prescription duration in addition to 1.5 times the number of days of supply of the last linaclotide prescription following its expiry date) plus one additional day when a potential discontinuation (or switching) could be assessed. Patients who continue taking linaclotide will be censored at the end date of the study period for linaclotide utilisation. This has implications for the interpretation of linaclotide treatment duration because it is conditioned by the study length.

Switching from linaclotide requires discontinuation in the prescription of linaclotide but these patterns will be considered exclusive events and patients experiencing switching immediately after discontinuation will be allocated to switching. Time to discontinuation and time to switching to another drug are secondary endpoints for the linaclotide utilisation study.

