4.7. Data Sources

The feasibility of conducting this utilisation study was assessed in the countries of interest and the most suitable databases identified that will be used in this study are the following three:

1. UK: the Clinical Practice Research Datalink (CPRD)

It contains information recorded by general practitioners (GPs) as part of their routine clinical practice and covers approximately 8% of the UK population. Core data include information on socio-demographic characteristics, diagnoses, symptoms, referrals, tests ordered, some test results, prescriptions issued, and additional clinical information. Prescriptions as prescribed by the primary care physician (PCP) or GP have fields for strength and dose. Medical data are coded using the Read coding system and, when linked to secondary care data from the Hospital Episode Statistics (HES), hospitalisation reasons for admission are coded by the International Statistical Classification of Diseases and Related Health Problems, 10th revision (ICD-10) and hospital tests and hospital procedures by operating procedure code supplement (OPCS) codes. The data available in the 2014, 12/14 static version of the database, included 474 research quality (acceptable) patients with at least one prescription for linaclotide.

2. Spain: SIDIAP

It is a primary care database that collects longitudinal data from electronic medical records (EMR) from 274 primary care centres in Catalonia since 2006, representing approximately 12% of the Spanish population. Data from primary and specialised care, hospital, and pharmacy are available, as well as patient characteristics, such as gender, date of birth, GP-diagnosed conditions, GP prescriptions, prescription dosing and size, date of prescription and dispensation, laboratory test results, other procedures, specialist referrals and diagnosis, hospital referrals, hospital procedures and discharge diagnoses, death date, and pregnancy information. GP diagnoses are coded following the ICD-10 codes, and hospital admissions following the International Statistical Classification of Diseases and Related Health Problems, ninth revision (ICD-9).

3. Sweden: the National Patient Registry (NPR) and Prescription Drug Registry (PDR)

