Information on diagnoses will be obtained from the Swedish NPR, which covers all public inpatient care since 1987 and all outpatient visits since 2001. The medical data include main and up to 21 secondary diagnoses and up to 30 surgical procedures from public and private service providers (National Board of Health and Welfare (Sweden), 2012). Diagnoses are coded using ICD-10 codes and surgical procedures with the Nordic Classification of Surgical Procedures. Primary care is not yet covered in the NPR. At present, the NPR is updated once a year.

Information about treatment use will be obtained from the Swedish PDR. Its coverage is close to 100% of all prescribed medicines from both primary health care centres and outpatient specialists dispensed to the Swedish population, and information is available since July 2005 (Wettermark et al., 2007). The register contains data on the substance, brand name, formulation, and package, dispensed amount, dosage, expenditure, and reimbursement as well as date of dispensing. Dispensation of over-the-counter (OTC) medications is not included.

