4.9. Data Analyses

All analyses will be first performed separately in each of the study countries. In addition, for the primary study objectives, aggregated analyses with data from all three countries will be performed.

Baseline analyses will be conducted to characterise linaclotide users, and socio-demographic and clinical variables will be described for all users and for those subgroups of patients who were not sufficiently documented in the clinical development programme. The number and percentage of patients using linaclotide off-label will be also described.

Further, linaclotide treatment patterns will be described from index date to end of study period for linaclotide utilisation. Kaplan-Meier estimates will be used to describe time to discontinuation in the prescription or dispensation of linaclotide; and to describe switching from linaclotide to another drug used in IBS-C (laxatives, antispasmodics, prokinetics, or antidepressants). To better assess differences in time to event by the alleged reason for linaclotide prescription (IBS-C or other condition), Cox regression analysis will be employed if the proportional hazards assumption holds; if not, more complex models will be proposed, including predictor variable interactions with time.

Statistical analyses will be conducted using SAS® statistical software.

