9.6. Data Management

We will collect electronic primary care patient records from the CPRD in the UK and electronic records on inpatient and outpatient admissions and dispensation of drugs in Sweden from the NPR and PDR. Routine procedures will include checking electronic files, maintaining security and data confidentiality, following analysis plans, and performing quality-control checks of all programmes. In Spain, SIDIAP will be in charge of the data management.

Each database custodian will maintain any patient-identifying information securely on site according to internal standard operating procedures. [REDACTED] will maintain the data cuts according to internal procedures.

An [REDACTED] data analyst will write and review programs to implement the analyses outlined in the Data Analysis section below. The project team will review all data output, including SAS® code as needed. Changes and corrections to programs stemming from the review will be made as appropriate. All programs will be saved and the process documented. Security processes will be in place to ensure the safety of all systems and data. Every effort will be made to ensure that data are kept secure so that they cannot be accessed by anyone except select study staff.

Appropriate data storage and archiving procedures will be followed (i.e., storage on compact disk read-only memory [CD-ROM] or digital versatile disk [DVD]) with periodic backup of files to tape. Standard procedures will be in place at each research centre to restore files in the event of a hardware or software failure.

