9.7.1. Patient Characteristics and Medical History

At linaclotide cohort entry date or index date, the socio-demographic characteristics of all linaclotide users, comorbidities, and the most relevant co-medications will be assessed by reviewing data for a minimum of 12-months prior to index date, and summary statistics will be reported with mean and standard deviation for continuous variables and number and percentage for categorical ones. The number and proportion of patients with missing data will be reported for each of the variables of interest.

Baseline characteristics will also be described in the following subgroups of patients, selected because in the clinical development programme, the use of linaclotide in these groups reflected important missing information, potential off-label use, and potential for abuse/excessive use:

- Children and adolescents (younger than 18 years of age)
- Older adult population (65 years or older)
- Pregnant or breast-feeding women

- Male patients
- Non-IBS-C patients with chronic constipation
- Patients with known or suspected mechanical gastrointestinal obstruction or IBD
- Patients with specific comorbidities (i.e., hepatic or renal impairment, cardiovascular diseases and associated risk factors, hypertension, diabetes)
- Patients with potential for abuse/excessive use—e.g., use for weight loss (patients with body mass index <20), use as a laxative (patients with codes for constipation only).

9.7.2. *Linacotide Prescription Patterns*

Linacotide treatment patterns will be assessed in the follow-up period from index date, as defined above.

The numbers and proportions of patients who experience one of the following treatment events will be reported separately:

- Discontinuation in the prescription of linacotide
- Switching from linacotide prescription to the prescription of another drug (i.e., laxatives, antispasmodics, prokinetics or antidepressants)

Switching from linacotide requires discontinuation in the prescription of linacotide but these patients will be allocated to switching so the two categories will be mutually exclusive. Kaplan-Meier estimates will be used to describe the times to first discontinuation or switching.

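### The baseline microbiology item groups patients without a test result with those who tested negative, so its percentage positive mixes how often results are recorded with what they show

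*Protocol*

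**What the plan says.** Protocol section 9.3.2 ends its list of baseline variables with "Bacterial/viral/parasite lab information, when available (positive versus negative or no information". Section 9.7.1 then sets a general reporting rule: "The number and proportion of patients with missing data will be reported for each of the variables of interest".

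Section 4.7 describes the sources unevenly on laboratory data:

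- **UK (CPRD):** core data include "tests ordered, some test results, prescriptions issued".
- **Spain (SIDIAP):** the contents include "date of prescription and dispensation, laboratory test results".
- **Sweden (patient register):** "The medical data include main and up to 21 secondary diagnoses and up to 30 surgical procedures from public and private service providers".
- **Sweden (drug register):** "The register contains data on the substance, brand name, formulation, and package, dispensed amount, dosage, expenditure, and reimbursement as well as date of dispensing".

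Section 9.6 describes the Swedish extract in the same terms, as "electronic records on inpatient and outpatient admissions and dispensation of drugs in Sweden from the NPR and PDR". None of the Swedish descriptions lists laboratory results.

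On pooling, the abstract (section 4.9) states that, for the primary objectives, "aggregated analyses with data from all three countries will be performed". Section 9.7 of the main text mentions only separate analyses by country.

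**The concern.** A patient never tested and a patient tested with a negative result are different observations, and the stated coding gives them the same value. The resulting percentage depends on two things: how often a result reaches the database, and how often a recorded result is positive. A reader of the table cannot separate them.

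Patient characteristics are a primary research question (section 8.1), and they will be shown for three countries with different recording. A gap between two countries on this item could come entirely from recording. The same holds if the variable were chosen for the Cox models of section 9.7.2, which admit various baseline variables: the reference group would mix negatives with untested patients.

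The coding also pulls against section 9.7.1. A two-level variable in which absence of information is a valid value has no missing category left to report. The protocol does not say which of the two statements governs.

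**Working it through.** **Inputs from the documents.** Table 3 (section 9.5) projects, for 2016, 2,674 patients in the UK, 2,407 in Spain and 4,584 in Sweden, 9,665 in all. Section 9.5 states the shares as about 28%, 25% and 47%.

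**Reproducing the stated shares.**

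- UK: 2,674 / 9,665 = 27.7%
- Spain: 2,407 / 9,665 = 24.9%
- Sweden: 4,584 / 9,665 = 47.4%

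These agree with the protocol.

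**Inputs not in the documents (assumptions).** Let *t* be the share of patients with a result on record and *p* the proportion positive among them. I take *t* from 10% to 100% and *p* from 5% to 20%.

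**Step 1: within one country.** Under the two-level coding, the reported percentage is *t* × *p*.

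| *t* | *p* = 5% | *p* = 10% | *p* = 20% |
|---|---|---|---|
| 10% | 0.50% | 1.00% | 2.00% |
| 30% | 1.50% | 3.00% | 6.00% |
| 50% | 2.50% | 5.00% | 10.00% |
| 100% | 5.00% | 10.00% | 20.00% |

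Two databases with the same positivity of 10%, one with results for 10% of patients and the other for 50%, would show 1.0% and 5.0%. The fivefold difference comes only from recording. Conversely, a reported 5.0% fits *t* = 50% with *p* = 10% as well as *t* = 100% with *p* = 5%.

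**Step 2: pooled, only if a database without results is included.** Suppose Sweden had no results and its patients were placed in the lower level. The pooled percentage would be (2,674 + 2,407) × *t* × *p* / 9,665 = 0.526 × *t* × *p*. At *p* = 10%:

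- *t* = 10%: 0.53%
- *t* = 30%: 1.58%
- *t* = 50%: 2.63%
- *t* = 100% in the UK and Spain: 5.26%

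Over the whole assumed range, the pooled figure runs from 0.26% to 10.51%.

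**Step 3: the missing-data rule.** The number without a result can be counted from the source records before the levels are merged. It cannot be recovered from the merged variable. Sections 9.3.2 and 9.7.1 can therefore both be followed only if the analyst keeps a third state that section 9.3.2 does not provide for.

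**The case against.** **The item may never have been meant as a prevalence.** It is listed as laboratory information under other variables. A recorded positive against everything else follows the logic of the code-based characteristics, where absence of a code means not recorded. Section 9.9 acknowledges that findings depend on the completeness of the records. This stands in part. It rules out calling the reported figure an understated prevalence, and positivity among the tested would not be an unbiased prevalence either, because testing is selective. It does not remove the mixing of two quantities in one percentage.

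**Section 9.7.1 is a safeguard.** If it is followed from the source data, the untested share would be disclosed. This is correct, and it would be wrong to say that missing results cannot be counted. What remains is that the stated coding does not lead an analyst there.

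**Sweden.** A reader might infer that every Swedish patient will be counted as negative and that nearly half of an aggregated denominator can never be positive. The documents do not support that as a fact. The line carries a when-available qualifier, which may mean that the item is omitted where a database lacks it. The absence of Swedish laboratory data is inferred from the listed contents and is not stated. Pooling appears in the abstract but not in section 9.7. The 47% is also a projection for 2016, and section 9.5 reports that actual counts fell below target in each database.

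**The analysis plan may settle it.** Annex 1 lists a separate one, which is not at hand. But the protocol itself states the levels, so this is a stated rule and not a detail left open.

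**Importance.** The variable is not in the subgroup list, the off-label objective or any named model term. That stands.

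**Conclusion.** The point holds in a limited form. As written, section 9.3.2 places patients without a result with those who tested negative. Whenever some patients are untested and some results are positive, the percentage positive over all patients lies below the positivity among the tested, by the factor *t*. This applies in the UK, where only some results are held, and in Spain to the extent that users have no result on record. It does not depend on how Sweden is handled.

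The Swedish and pooled effect is conditional. Only if a database without results is kept in and pooled would up to 47% of the projected denominator be unable to be positive, with a further factor of 0.526.

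No single size can be given, because *t* and *p* are not in the documents; the worked percentages are illustrations over assumed ranges. The consequence is minor: one descriptive baseline item, on which no stated conclusion rests.

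**What to change.** In section 9.3.2, define three levels: positive, negative, and no result available. In the baseline tables, give for each country the number tested and the percentage positive among the tested, labelled as positivity among tested patients and not as prevalence. For any database without laboratory results, show the item as not available and leave that database out of any aggregated denominator for this item. State explicitly whether this applies to Sweden.

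This brings sections 9.3.2 and 9.7.1 into agreement and needs no new data. The cost is a line of wording, one extra table row, and a smaller denominator made up of selectively tested patients. For that reason the number tested must stand beside the percentage.

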SIDIAP is a primary care database launched in 2010, following the steps of CPRD or THIN in the UK, that collects longitudinal data from EMR from 274 primary care centres in Catalonia since 2006. Catalonia is a region with a total of 5.8 million patients who represent approximately 12% of the Spanish population (4% of the Spanish population in SIDIAP-Q with higher quality indicators). Data is updated once a year and there are several scientific publications using this data source and reporting validation study results. The date of the latest available data is December 2013, and 2014 data will be made available by May–June 2015.

Data from primary and specialised care, hospital and pharmacy data are available, as well as patient characteristics such as gender and date of birth, GP-diagnosed conditions, GP prescriptions, prescription dosing and size, date of prescription and dispensation, laboratory test results, other procedures, specialist referrals and diagnosis, hospital referrals, hospital procedures, and discharge diagnosis death rate, and pregnancy information. GP diagnoses are coded following the ICD-10 codes, and hospital admissions following the ICD-9.

SIDIAP does not transfer data to private entities, but it can carry out quality investigation projects (Bolívar et al., 2012) and submit on their completion the corresponding reports on results, which will be agreed upon with the funding body in the design stage of the study. It also allows the possibility to contact physicians (currently a group that includes 10% of the total) for extracting additional information on the patient through a questionnaire.

SIDIAP is considered to be an appropriate source of data for the execution of this as the vast majority of its patients have two and three or more years of follow-up and the database itself can link with the Drug Dispensation databases (and additionally with the Mortality Registry for Death Cause); both characteristics are relevant for the proposed linaclotide study. The objectives were reviewed by their research team who are confident about the utilisation study. They identified some challenges for the safety study, and recommended performing a preliminary descriptive and exploratory study to confirm feasibility of conducting the study and to improve the validity of the actual study results.

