- Clinical information including main diagnosis (ICD-9-CM), secondary diagnosis (up to 10 different diagnosis), medical/ surgical procedures (up to 10 different surgical procedures, ICD-9CM)
- Cost information including diagnostic-related group (all patients diagnostic-related groups) and estimated inpatient cost

The primary care database accounts for at least two million people every year. This data source is built entirely from real data and covers 100% of four (out of a total of 17) different autonomous communities (regions) in Spain. Due to confidentiality reasons IASIST cannot provide any further information on the areas that are being covered.

Major limitations for the purposes of this study data are that patients cannot be tracked across different hospitals as patient identification numbers are designated by every region and every year. For the same reason, patients cannot be tracked longitudinally over time. Additionally, primary care data cannot be linked to secondary care given that information is provided to IASIST by each provider separately and patient identification is done separately by each provider. Therefore, this data source was not considered appropriate and was excluded.

Sweden

In Sweden, there exist several registries with high quality data and large coverage of the population. Given that for this study one of the main challenges were related to accrual of sufficient sample size, only national registries were considered. The two registries that have been proposed for this study include diagnosis and medications and could be linked together through a unique patient identifier:

Proposed Data Source: The National Patient Register

The Swedish National Patient Register (NPR) was initiated in 1964, initially covering inpatients in six county councils in Sweden. Since 1987, the register covers all public inpatient care and all outpatient visits since 2001. Data on primary care is not available. The information in NPR can be divided into 4 different groups covering several variables each: 1. Patient data; 2. Geographical data; 3.

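### The entire-history look-back in 9.3.2 has no recency rule, so a resolved mechanical obstruction (and, less clearly, a past eating disorder) counts as status at index, over record lengths that differ by database

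*Protocol*

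**What the plan says.** Section 9.3.2 opens with a general rule: "Patients included in the DUS will be described according to their characteristics at index date, using data from the baseline period". It then lists the baseline variables, including mechanical gastrointestinal obstruction and obesity and eating disorders. It closes with a special rule: "For prevalence of chronic comorbidities, prior diagnoses, or history of digestive surgery at index date", "the patient's entire medical history will be explored".

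Section 9.2.2.2 defines the baseline period as at least 12 months before index and sets no upper limit. Section 9.7.1 does the same: comorbidities are assessed by "reviewing data for a minimum of 12-months prior to index date".

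Section 9.7.1 names the subgroup "Patients with known or suspected mechanical gastrointestinal obstruction or IBD". Section 8.2 asks for the number and percentage of patients with potential for off-label, abusive or excessive use among those with eating disorders. Section 9.3.1 describes eating disorders as conditions suspected to relate to that potential.

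Annex 3.B gives the record lengths. CPRD has an average follow-up of 10 years. SIDIAP collects data "from 274 primary care centres in Catalonia since 2006". For the Swedish NPR, "Since 1987, the register covers all public inpatient care and all outpatient visits since 2001". Section 4.9 plans aggregated analyses across the three countries for the primary objectives, after separate analyses by country.

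**The concern.** The baseline table is meant to describe patients at the moment they start linaclotide, and the obstruction subgroup is worded as a present state. An unlimited look-back suits chronic conditions such as IBD or diabetes, and it suits past surgery. It does not suit a condition that can resolve, because a single old episode then puts the patient in the same cell as someone with a current problem. (That obstruction and eating disorders can resolve is general knowledge, not a statement in the Protocol.)

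Two things are at stake. First, the study looks at these subgroups because they reflect missing information, potential off-label use or potential for abuse, and an ever-recorded flag cannot separate recent from remote obstruction. Second, the look-back is as long as each database happens to be. Identical patients can be classified differently in the UK, Spain and Sweden, and the aggregate then mixes these definitions. Section 9.9 does not list this as a limitation.

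**Working it through.** **Step 1: which window applies?** There are two candidate readings.

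- The special rule in 9.3.2 covers prior diagnoses. Obstruction and eating disorders are diagnoses in that section's own list, so on a plain reading the whole record is searched.
- The general rule points to the baseline period, which 9.2.2.2 and 9.7.1 bound only from below.

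Neither reading sets a maximum look-back or asks for a recent or active code.

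**Step 2: how long is the record at index?** Index dates run from launch (9.2.2.2) to December 2017.

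- UK, CPRD: about 10 years. This is an average over the whole database, used here as a proxy for look-back among linaclotide users.
- Spain, SIDIAP: 2006 to September 2014–December 2017, about 8 to 12 years.
- Sweden, NPR inpatient: 1987 to February 2013–December 2017, about 26 to 31 years.
- Sweden, NPR outpatient: 2001 to the same dates, about 12 to 17 years.

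**Step 3: illustration of how the flag depends on record length.** The Protocol gives no figure to reproduce and no incidence or duration. Assume a constant first-record rate λ of 0.1% to 1% per year and equal capture everywhere. The share ever recorded in L years is 1 − exp(−λL). The share first recorded in one year is 1 − exp(−λ). For λ = 0.1% and L = 10, that is 0.995% / 0.09995% = 9.96.

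| Record | L (years) | Ever / one-year, λ = 0.1% | Ever / one-year, λ = 1% | Relative to CPRD |
|---|---|---|---|---|
| SIDIAP, short end | 8 | 7.97 | 7.73 | 0.80–0.81 |
| CPRD, average | 10 | 9.96 | 9.56 | 1 |
| NPR outpatient | 16 | 15.88 | 14.86 | 1.55–1.59 |
| NPR inpatient, short end | 26 | 25.68 | 23.01 | 2.41–2.58 |

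The last column divides each ratio by the CPRD ratio at the same λ (for example 25.68 / 9.96 = 2.58). It shows how far apart identical populations could look from record length alone.

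**Step 4: ever-recorded against truly current disease.** If the condition lasts D years, current prevalence is about λD, and the ratio of ever recorded to current is about L/D. If only a fraction s of cases is captured, it is about s·L/D. For L = 10:

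| D (years) | s = 1 | s = 0.25 |
|---|---|---|
| 1 | 10 | 2.5 |
| 3 | 3.3 | 0.83 |
| 5 | 2.0 | 0.5 |
| 8 | 1.25 | 0.31 |

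D and s are assumptions. The ratio falls on both sides of 1, so the net error can be an overstatement or an understatement.

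**The case against.** The best reply has four parts.

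- **The rule does not name these conditions.** It names neither obstruction nor eating disorders, and condition-level windows often sit in a SAP. The first half is true. However, the Protocol itself fixes an entire-history look-back for prior diagnoses, so the point concerns what it states and not something it leaves out.

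- **Overstatement is not shown.** A reader might infer that use in patients currently at risk is overstated by something like the 8- to 26-fold ratios in Step 3, or that Sweden must show the highest percentage. The documents support neither. Those ratios compare ever recorded with newly recorded in one year, so they measure overstatement of current disease only if the condition lasts about a year. The largest applies only to Swedish inpatient diagnoses. Section 9.9 also states that Sweden has no primary care diagnoses and that only comorbidities for which the patient consulted the GP are identified. That under-capture could offset or reverse the effect. This part of the objection stands.

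- **Past eating disorders can be relevant.** The plan uses them as a marker of potential for abuse, and the 9.7.1 abuse subgroup is exemplified by low body mass index and constipation-only codes. A reader might infer that a remote eating disorder is wrongly counted; the text does not say that only current disease is the target. This stands, and the point is therefore weaker for eating disorders than for obstruction.

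- **Broad ascertainment is defensible, and countries are first reported separately.** Both are true. They argue for keeping the ever-recorded count, not against showing a recent count beside it. Among recorded cases the ever-recorded flag can never be lower than the recent one, and separate reporting does not give the countries a common window.

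**Conclusion.** The point holds in a limited form. As written, any ever-recorded episode of a condition that can resolve counts as status at index. The affected group is chiefly mechanical obstruction and, to a lesser extent, eating disorders. Look-back length is set by the database, from about 8 years at the short end in SIDIAP to more than 25 years for Swedish inpatient data, so the country percentages and their aggregate do not rest on one definition.

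The direction and size of the net error cannot be derived from the documents. Under the stated assumptions (constant rate, equal capture), record length alone could move a Swedish figure to about 1.6 times the UK one for outpatient diagnoses and about 2.4 to 2.6 times for inpatient diagnoses. Unequal capture could shrink or reverse that. The conclusion rests on reading prior diagnoses to include both conditions, which is natural but not explicit. This is an inexpensive improvement to interpretability, not a flaw that invalidates the study.

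**What to change.** In 9.3.2 and 9.7.1, keep the ever-recorded row. For mechanical obstruction and for eating disorders, add a separate row for a code within the 12 months before the index date, in all three databases. Every patient has this window, because 9.2.2.1 requires at least 12 months of computerised records. Use the 12-month row for cross-country comparison and for the aggregate in 4.9, and label the ever-recorded row with each database's record length. Leave the entire-history rule in place for chronic conditions and digestive surgery.

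Add to 9.9 that look-back length and diagnostic capture differ between databases. A common window removes the first difference but not the second.

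The cost is a sentence in each section and one extra row per condition, from records already being searched. The 12-month counts will be smaller, and ongoing disease not re-coded in the last 12 months will appear only in the ever-recorded row, which is why both rows are needed.
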